#### Addendum:

The comparators as used in this proposal address the magnitude of gaps across 5 healthcare quality dimensions as experienced by people at each of 4 stages of disability in comparison to those without disabilities, and the implications of those quality gaps to risks of functional deterioration. The health care quality dimensions as assessed by the patient include 1) Care coordination and quality, 2) Access barriers, 3) Technical skills of the PCP, 4) Interpersonal skills of the PCP, 5) Quality of information provided by the PCP.

PRINCIPAL INVESTIGATOR (LAST, FIRST, MIDDLE): [name]

---

## APPENDIX

*(Use continuation pages as needed to provide the required information. Note that the Appendix is optional.)*

---

#### Appendix B: Draft demographic survey

DRAFT SURVEY FOR PWD and family members. May be completed with the help of a proxy

PRINCIPAL INVESTIGATOR (LAST, FIRST, MIDDLE): [name]

(guardian, family caregiver, non-family caregiver, interpreter, etc., as an ADA accommodation). Note: Versions will be developed for family and non-family caregivers and clinicians with similar content. The clinician version will be designed to focus on describing the population they treat.

1- Do you have any difficulty with any of the following self-care activities (check all that apply)?

- Eating
- Using the toilet
- Dressing
- Bathing or showering
- Transferring (getting in and out of bed or chairs)
- Walking
- Other problem (Describe \_\_\_\_\_)

2- Do you have difficulty with any of the following independent living activities (check all that apply)?

- Managing money (keeping track of expenses or paying bills)
- Preparing own meals
- Doing light housework (straightening up, light cleaning or dishes)
- Shopping for personal items (such as toilet items or medications)
- Using the telephone
- Doing heavy housework
- Other problem (Describe \_\_\_\_\_)

3- Do you see yourself as a

- Person with disability?
- Family member caregiver? Request form for family member caregiver.
- Non-family caregiver? Request form for non-family caregiver.
- Health professional? Request dates for health professional stakeholder group.
- None of these? You are not eligible to participate in this study.

4- Gender (Check all that apply)

- Male
- Female
- LGBT (Lesbian/Gay/Bisexual/Transgender)
- Choose not to disclose

5- How old are you?

- 21- 30
- 31-40
- 41-50
- 51-60
- 61-70
- 70-80
- 81 or older
- Choose not to disclose

6- Partnership or marital status

- Married or currently partnered
- Single or currently alone
- Widow, widower, divorced, or previously partnered
- Choose not to disclose

PRINCIPAL INVESTIGATOR (LAST, FIRST, MIDDLE): [name]

7- Do you live alone?

- Yes
- No

8- Because of your disabilities, do you have problems with the following? Select all that apply to you:

- Cognition (Intellectual functions such as memory, knowing time and place)
- Mental health (Emotional, social functioning)
- Hearing (Deaf)
- Seeing (Blind)
- Chronic fatigue
- Pain
- Communication (Voice, speech, expression and understanding)
- Cardiovascular or respiratory
- Digestive (problems with bowels or stomach)
- Genitourinary/kidney (problems with urination, renal dialysis)
- Sexual function
- Movement related (Joints or bones including back)
- Movement related (muscle power/paralysis)
- Other (please specify) \_\_\_\_\_
- Choose not to disclose

9- Is your disability visible (Will people notice it when looking at you or talking with you?)

- Yes
- No
- Choose not to disclose

10- Was your disability present at birth?

- Yes
- No
- Chose not to disclose

PRINCIPAL INVESTIGATOR (LAST, FIRST, MIDDLE): [name]

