#### ***Choice of the Stakeholder Study Population***

We chose to recruit PWD, family members, and PWOD from two populations. The Virtual Ability Island community (VAI) was selected because it is a well-established world-wide online virtual community designed by and for people with a wide range of physical, mental, sensory, and intellectual disabilities. VAI operates within several virtual worlds, including a long-established (2003) commercial, publicly available, free 3D graphic environment called Second Life (SL) with millions of users. SL "residents" are avatars, controlled by people from all walks of life who live, work, and play within the virtual world. VAI empowers and helps PWD move beyond the barriers separating them from the larger society. People come from many diverse cultures across the age spectrum, and frequently share innovative grassroots solutions to living autonomously, making VAI ideal for community-engaged research. Groups formed within VAI will be referred to as the "**VAI groups**." Yet, access to VAI requires the ability to use computers which are not accessible to all PWD. Concerned that VAI might not be representative of the larger population of PWD, we will also recruit from a low income integrated supportive urban community housing project run by Jewish Family Services (JFS) Housing, Inc. This population of adults is located in two buildings, Bradley Crossing and Deerwood Crossing, in Milwaukee, WI. This second cohort will include a high proportion of ethnic minorities with educational challenges and low computer literacy. Groups of these individuals will be referred to as the "**Urban groups**." Additionally, clinician stakeholders will be recruited from Second Life and referred to as the "**Clinician groups**." VAI and Clinician groups together compose the "**SL groups**" since they will both be convened within Second Life.

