#### ***Selection Criteria for CBPR and Qualitative Study***

Each VAI and Urban group will include 4 to 6 PWD, 1 or 2 PWOD, and 1 or 2 caregivers. Clinician groups will be separate and will also consist of about 6 to 8 individuals per group. PWD will be defined as being at ADL- and/or IADL-I, II, III, or IV, and PWOD as being at ADL- and IADL-0. Clinicians must be clinically active health professionals (nurse, physician, physical therapist, and others). Inclusion criteria are: 1) Age 21 years old or older and living in a US community; and 2) The ability to communicate and participate in small group dialogue online (VAI groups) or in-person (Urban groups) with or without an Americans with Disability Act (ADA) accommodation.

Sampling will be purposive to ensure enrollment of people from diverse socioeconomic circumstances and across the broad spectrum of disability type and severity. Participants for the VAI groups will be recruited through the VAI membership of over 700 PWD and 175 caregivers of PWD, building on protocols established and applied extensively in Second Life by our

PRINCIPAL INVESTIGATOR (LAST, FIRST, MIDDLE): [name]

consultant [name]. Participants in the Urban groups will be recruited from JFS Housing, Inc. (with about 135 PWD) through community newsletters and community meetings. Clinicians will be recruited through Second Life. The stakeholder consultant ([name]) personally has about 100 medical professional contacts within Second Life including nurses, paramedics, physicians, midwives, occupational therapists, and mental health counselors belonging to over 60 Second Life health professional groups.

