The PCP quality comparators were less strongly related to 1-year transitions. Poorer PCP interpersonal skills were associated with functional deterioration (p=.01) and 1-year mortality (p=.003). Patients’ perceptions of poorer PCP interpersonal skills were marginally associated to institutionalization (p=.07). Poorer quality of information provision was related to institutionalization (p=.04). These findings provide powerful support for this study.

**Stakeholder interpretation:** Stakeholders found all findings logical except linkage between poorer perceived healthcare access and quality and functional improvement. They had the following thoughts and questions: Being angry with poor access and low quality healthcare might motivate functional improvement. Those who improved functionally might be more motivated to fight for better care. Will these findings persist after statistical adjustment and analyses across a decade and timeframe of 3 years? What other factors, potentially discoverable through stakeholder engagement, might explain this startling finding?

**AIM 1: Where do we see the problems?** Aim 1 seeks to uncover themes related to the 5 comparators and stakeholders’ perceptions on whether or not they experience healthcare and PCP quality problems and if those problems impact transition outcomes. PWD, PWOD, and families, in VAI and Urban groups, will address the following kinds of questions in a focus group format: *How does access and quality of healthcare received differ for PWD and PWOD? How does poorer quality healthcare impact risks of functional decline, institutionalization, or death?* The Clinician groups will address identical questions but relative to their clinical practices.

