#### **Research procedures**

After giving consent, participants will be asked to complete a survey which will determine eligibility for inclusion. Prior to attending a focus group, participants will be asked: 1) their age (decade), 2) marital status, 3) gender, 4) whether they have disabilities or are caring for someone with disabilities (family member, paid caregiver, health professional). Focus group participants will be asked to indicate the broad type(s) of disabilities they (or the person they care for) has. Finally, they will be asked if their disability (or the disability of the individual for whom they are providing care) is obvious (can be seen) or is hidden. The participant can complete the survey with or without ADA accommodations, depending on need.

PRINCIPAL INVESTIGATOR (LAST, FIRST, MIDDLE): [name]

Once the survey has been completed, the participant will receive information about the time, date, and location of a focus group. Each participant who completes a focus group in Second Life will be gifted 1000 Linden dollars (currency used in Second Life, valued at about \$4.85) and each participant in a face-to-face focus group will receive a gift card to Target or Walmart worth \$5.00 to compensate for participation.

Risk of loss of subject confidentiality is minimal to nonexistent. Neither real names nor any information that might be used to track individuals will be sought or included in the study records. The only contact between focus group participants and study personnel will be through confidential focus group discussions using masked-identity avatars in SL and appropriate confidentiality procedures at JFS Housing, Inc.

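### Item 3 of the draft Appendix B survey turns away people without disabilities for whom the selection criteria reserve places in each VAI and Urban group

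*Combined protocol and SAP*

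**What the plan says.** The section Selection Criteria for CBPR and Qualitative Study fixes the make-up of the groups: "Each VAI and Urban group will include 4 to 6 PWD, 1 or 2 PWOD, and 1 or 2 caregivers". It then defines the two kinds of people by function: "PWD will be defined as being at ADL- and/or IADL-I, II, III, or IV, and PWOD as being at ADL- and IADL-0". The criteria begin: "Inclusion criteria are: 1) Age 21 years old or older and living in a US community". The second criterion is being able to take part in a small-group discussion, online or in person. Neither criterion requires a role.

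Two other places name PWOD as participants. Choice of the Stakeholder Study Population says: "We chose to recruit PWD, family members, and PWOD from two populations". The Aim 1 paragraph says: "PWD, PWOD, and families, in VAI and Urban groups, will address the following kinds of questions".

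Item 3 of Appendix B offers four self-descriptions: person with disability, family caregiver, non-family caregiver and health professional. Everyone else reads: "None of these? You are not eligible to participate in this study". The form is headed as a draft for PWD and family members. A note promises further versions for family caregivers, non-family caregivers and clinicians.

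Two passages bear on how the form is used. Research procedures, in the human subjects section, says that after consent "participants will be asked to complete a survey which will determine eligibility for inclusion". Group procedures, in the Project Plan, has all stakeholder participants fill in the Appendix B survey.

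**The concern.** The selection criteria and the form apply different rules to the same people. The criteria classify by stage and admit PWOD as a category of their own. Item 3 classifies by self-image and has no eligible answer for a person who is neither disabled in their own view nor in a caring or clinical role.

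Aim 1 asks the groups how access and quality of care differ between PWD and PWOD. If item 3 were followed as drafted, the only PWOD able to speak to that question in VAI and Urban groups would be caregivers or people who regard themselves as disabled. PWOD outside those roles would be missing from the transcripts that generate hypotheses. Some people whom the criteria count as PWD could be turned away as well, and because the survey follows consent, this would happen after they had agreed to take part.

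**Working it through.** The plan gives no total for PWOD places, so there is no figure to reproduce. The check has two parts: the two rules set side by side, and a count of places.

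**1. The two rules compared.** Table 1 puts a person at stage 0 only if none of the six ADLs and none of the six IADLs is difficult. Items 1 and 2 of Appendix B list the same 6 + 6 = 12 activities, plus a free-text line that plays no part in staging. Any listed activity ticked therefore means stage I or above (PWD); none ticked means stage 0 on both scales (PWOD).

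| Person (age 21 or over, US community, able to take part) | Selection criteria | Item 3 |
|---|---|---|
| Stage 0, not a caregiver or clinician, does not see self as disabled | Eligible, PWOD | Turned away |
| Stage 0, sees self as disabled (for example, deaf) | Eligible, PWOD | Passes |
| Stage 0 caregiver | Eligible; stage 0, but caregivers are counted separately | Passes to the caregiver form |
| Stage I-IV, sees self as disabled | Eligible, PWD | Passes |
| Stage I-IV, does not see self as disabled, no other listed role | Eligible, PWD | Turned away |

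The rules disagree in the first and last rows. Health professionals are routed to the separate Clinician groups and are not at issue.

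**2. Count of places.** Inputs:
- PWOD per VAI or Urban group: 1 to 2 (Selection Criteria).
- Aim 1 groups: 3 VAI and 1 Urban (Aim 1 text; Table 7).
- All groups: 8 VAI and 3 Urban (Analytic Methods (General)).
- Group size: 6 to 8 people (Table 7).

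Places = number of groups × PWOD per group.
- Aim 1: (3 + 1) × 1 to 2 = 4 to 8 places, among 4 × 6 to 8 = 24 to 32 people.
- All VAI and Urban groups: (8 + 3) × 1 to 2 = 11 to 22 places.

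These are ceilings on the PWOD places touched. The floor is 0: rows two and three of the table show stage-0 people who pass item 3 and might fill every place. The number of stage I-IV people turned away cannot be derived, because the documents do not say how often such people decline the label.

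**The case against.** The strongest reply is that this is an unfinished form. Appendix B is marked as a draft throughout and headed for PWD and family members. The Project Plan, Table 8 and the subcontract task list all schedule stakeholder rewriting of the questions and forms. That stands, and it lowers the severity. It does not remove the conflict. The exit in item 3 speaks of the study, not of this version of the form, and the further versions named are for caregivers and clinicians only.

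Second, the link between Appendix B and eligibility is partly inferred. Research procedures does not cite Appendix B when it describes the eligibility survey, and it lists different questions, none of which excludes anyone. This also stands. The screening force comes from item 3's own wording and from Group procedures, which applies Appendix B to all stakeholder participants.

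Third, the planners may have meant stage-0 caregivers to supply the PWOD voice. The VAI recruitment text points that way: "Participants for the VAI groups will be recruited through the VAI membership of over 700 PWD and 175 caregivers of PWD". It gives no pool of PWOD, and the Project Plan describes the Aim 1 groups more loosely, joining PWOD and caregivers with an and/or. That reading is fair and explains why the loss may be nil. It does not fit the group composition in the selection criteria, where the two are counted separately.

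Fourth, items 8-10 presume a disability, but they block nobody: item 8 can be left blank and all three offer a non-disclosure answer. This is a matter of wording only.

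A reader might also infer from Part A, which reports that patients rarely reveal their true feelings about functional loss, that self-description is a weaker screen than the activity items. The documents do not support that. The remark concerns feelings, not the label of disability, and items 1 and 2 are self-reported too. The reason to prefer them is only that the selection criteria define status by stage.

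**Conclusion.** The conflict between item 3 and the selection criteria is real and needs reconciling. Its reach is small: the counts above are upper limits on places, not estimates of people lost.

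A reader might go further and conclude that the groups will contain no PWOD, or that the comparison of PWD with PWOD is compromised. Neither follows. Stage-0 caregivers and stage-0 people who see themselves as disabled still pass item 3. The quantitative comparison is made in the Medicare Current Beneficiary Survey, which does not use this form, so those analyses and their power are untouched. The effect is confined to a purposive qualitative sample that the plan itself describes as not generalizable.

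The conclusion assumes that the draft is used unchanged and that it serves as the eligibility screen. Appendices A and D, which the recruitment plan cites for joining, were not in the text available for review and may bear on this. I rate the point minor, with moderate confidence.

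**What to change.** - In item 3, replace the ineligible exit with an eligible answer such as Person without disability.
- State that PWD or PWOD status is assigned from the 12 activities in items 1 and 2 by the stage rule in the selection criteria: any ticked is PWD, none ticked is PWOD, and the free-text line is not counted.
- Let anyone who gives the new answer skip items 8-10, whatever they ticked in items 1 and 2. Alternatively, reword those items neutrally and add a not-applicable option. Tying the skip to having ticked nothing would leave a stage I-IV person who does not feel disabled facing questions about their disabilities.
- If the sponsor does not intend to recruit PWOD who are not caregivers, leave item 3's exclusion of them in place. Change Choice of the Stakeholder Study Population, the selection criteria and the Aim 1 text to say so, and still settle how stage I-IV people who decline the label are handled.

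The cost is a small edit to a form still in draft, with IRB approval pending and stakeholder revision of the forms already scheduled. It adds no data collection beyond one answer option. More people may pass the form than there are PWOD places, so facilitators would need to hold PWOD to 1 or 2 per group.

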## Appendix E: Draft stakeholder group guide with example questions and probes

Thank you for agreeing to participate in our study. We are very interested in knowing, based on your experience, ideas, and opinions, what you think about the qualities of the healthcare system and physicians in the US, particularly as related to those of us with disabilities. Once you participate in this group, you are considered a stakeholder participant and we hope that you will continue to be involved in the project. Follow findings on the website. Contribute further ideas to the blog. Tell your friends, family, and healthcare providers about what we are learning about the quality of healthcare provided to people with disabilities. But please remember you must not discuss the specific stories you hear outside of this focus group. We hope you enjoy the process.

Note: All groups will end with the following question:  
How well did this process work for you?

Example questions for stakeholders:

**DESIGN PHASE:** Help translate questions and forms (for use in groups) enhancing clarity, cultural appropriateness, and accessibility to low literacy participants: (about 6 VAI and 6 Urban participants).

- What are your views about this question?
- What do you see this question as asking?
- With this question, what sorts of things go through your mind?
- How would you make this question easier to understand?
- How important is this question?
- Are there other important questions?

**HYPOTHESIS GENERATION:** Themes related to the 5 comparators and perceived impact on status transitions (3 VAI, 1 Urban, 2 Clinician groups).

- How would poor quality healthcare, access, or coordination affect your chance of continuing to care for yourself and live independently? Please give examples.
- How would the skill and inter-personal manner of your primary healthcare provider influence your chance of continuing to care for yourself and live independently? Please give examples.
- Please describe how your physician's ability to provide important information for your health is essential to your ability to care for yourself and live independently. Please give examples.

**INTERPRETATIONS:** React to and help interpret quantitative findings as discovered through analysis of the MCBS relative to evidence of comparator effects on actual status transitions in populations of people at different stages of disability (reactions to Aims 2 and 3 findings). This will include 3 VAI, 1 Urban, and 1 Clinician Group

- How would you explain these findings to a friend or family member (tests participants' understanding)?
- What do you think of these findings?
- What makes sense to you?
- What surprises you?
- How would you present these findings more clearly?

PRINCIPAL INVESTIGATOR (LAST, FIRST, MIDDLE): [name]

**RECOMMENDATIONS:** As supported by simulations and summary of all findings, discuss strategies to encourage appropriate changes in the structure of the healthcare system targeted to enhancing the wellbeing of people with disabilities (reactions to Aim 4). The following example scenario reflects our preliminary findings (2 VAI, 1 Urban, and 1 Clinician group).

*“Our research shows that when people who have disabilities receive high quality healthcare that this may reduce the chance of their disabilities getting worse, reduce chances of their needing to go to a nursing home, and increase how long they live.”*

- Why do you think this is?
- What ideas do you have about improving healthcare quality for people with disabilities?
- What healthcare programs are most essential to helping people live independently and maintain their autonomy?
- If you could change one thing about the health services you receive, what would it be?
- People during earlier groups shared the following views and ideas about quality and access issues: (Key illustrative quotes from dominant themes will be provided.) What healthcare improvements would be most compatible with these ideas about quality issues?
- How could your doctor implement these improvements?
- What are the most important findings that we need to share with communities of people with disabilities, family members, clinicians, and policy makers?
- How would you describe these findings in your own words?
- How are these findings important?

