#### **Preliminary findings:**

Our preliminary work established strong partnerships between stakeholders and scientists. The stakeholder and scientist teams contributed equally to this proposal, generating ideas, creating and finalizing the specific Aims, establishing the initial protocol, interpreting preliminary findings, running groups in Second Life, and establishing a shared timeline.

**Qualitative and CPBR:** The stakeholder and scientific teams had multiple group meetings in Second Life where they worked on protocol design, interpretation of the preliminary results, and all other project preparations. The PI and stakeholder consultant ([name] and [name]) ran 4 pilot peer support groups in VAI on the inaccessibility of medical equipment and

PRINCIPAL INVESTIGATOR (LAST, FIRST, MIDDLE): [name]

services (see example of de-identified “chat” in Appendix C). The “public abstract” was written iteratively partnering between the stakeholder and quantitative analytic teams. We reached our readability goal at or below the 6th grade level. Readability was estimated by the Flesch-Kincaid Grade Level score, which was approximately at grade 5.5 based on the USA educational system.

**Quantitative:** Using MCBS data from 3 panels active at the time of the Fall interview in 2005 (N=10,399) and with complete information, we applied a multinomial logistic regression model studying 1-year transition outcomes (2006 on the 4-level transition outcome with no change in function being reference). The global quality comparator was most consistently associated with outcome transition. Poorer perceived healthcare was significantly associated with 1-year, functional deterioration, institutionalization, and mortality (all p-values ≤0.03). Poorer perceived healthcare quality was strongly associated with functional improvement (p=.0001). Both functional improvement and deterioration were strongly associated with poorer access (both p<.0001). Perceptions of poorer access were also associated with death at 1 year (p=.02).

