Six focus groups (3 VAI, 1 Urban, and 2 Clinician) will participate. Participants from Second Life (VAI and Clinicians) will be assured that their off-screen identities will remain confidential. Once people provide informed consent, they will be given entry into a private chat room on VAI property at a specific date and time. All of the focus groups will be led by a stakeholder co-investigator with personal knowledge about living with disability. The group leader’s role will be to pose questions in a standardized manner, moderate the discussion, move the discussion along, and keep the discussion safe for all participants. (See draft instructions for stakeholder focus groups in Appendix A). Prior to participation, each participant will be asked to complete a survey about disability(s) and life circumstance (See draft Appendix B). For groups in the virtual world, true identities will be masked behind created avatars (personas that individuals choose to represent themselves); in face-to-face Urban groups, members and their disabilities are known to each other. Text-to-speech software will be available to those who have low literacy.

Participation in the SL focus groups will generate “chat” in the form of typed dialogue (see Appendix C for an example). Participants’ characteristics (derived from the pre-group questionnaire) will be linked to their screen or avatar name (but not their actual identity). The

PRINCIPAL INVESTIGATOR (LAST, FIRST, MIDDLE): [name]

dialogue will be downloaded into document form and entered into QSR NVivo 10.0 for coding and analysis. The Urban group will use the same discussion guide as in the SL groups. Groups will be conducted in a private room. Because in-person focus groups are, by nature, only semi-private, we cannot assure confidentiality, but we will ask all group members to respect the confidentiality of group participants. Individual identities will not be revealed outside the group. All focus group results will be reported in the aggregate and we will not link an individual's name with anything s/he said. In-person focus group proceedings will involve a captionist as an ADA accommodation for deafness. This automatically generates a verbatim transcript which will be entered into NVivo 10.0 software along with chat from the SL groups for coding and analysis.

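### The draft Aim 1 questions in Appendix E take an effect of care quality for granted and pair up four of the five comparators, which tilts answers and weakens separation of the comparators

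*Combined protocol and SAP*

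**What the plan says.** The Aim 1 paragraph of the Research Strategy sets out to uncover themes on the five comparators and stakeholders' "perceptions on whether or not they experience healthcare and PCP quality problems and if those problems impact transition outcomes". It gives two example questions. One compares people with disabilities (PWD) and people without (PWOD): "How does access and quality of healthcare received differ for PWD and PWOD". The other asks how poorer care affects the risk of decline, institutionalization or death. Clinician groups are to take the same questions in relation to their own practice.

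Appendix E, a draft guide with example questions, lists three questions for the hypothesis-generation groups (3 VAI, 1 Urban, 2 Clinician):

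- Question 1: "How would poor quality healthcare, access, or coordination affect your chance of continuing to care for yourself and live independently".
- Question 2 asks how the primary care provider's skill and interpersonal manner would influence the same chance.
- Question 3: "Please describe how your physician's ability to provide important information for your health is essential to your ability to care for yourself" (it goes on to living independently).

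Each asks for examples. The Aim 1 procedures say that group leaders will "pose questions in a standardized manner", and that the Urban group uses the Second Life groups' discussion guide. Before Aim 1, one VAI and one Urban group help rewrite the questions. The stated purpose, under 'Reducing low literacy barriers', is readability.

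**The concern.** An aim framed as whether problems occur and whether they matter needs prompts that let a participant say no. These prompts ask how an effect works, and the third declares the provider's information essential before anyone has spoken. A participant who has met no problem, or who met one that made no difference, has to argue against the question to say so.

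The paired questions add a second difficulty. An answer to Question 1 may concern coordination and quality, or access, or both. Question 2 has the same ambiguity between technical and interpersonal skills.

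The output is used downstream. Table 9 has the Aim 1 themes revising the Aims 2 and 3 hypotheses at month 11 of Year 1. The general approach to analysis lets emergent themes guide the choice of covariates, and stakeholder input helps select candidate variables for the Surveillance Tool. The member-checking section adds that associations which look counter-intuitive may be left out of the Tool, and its example is poorer perceived quality going with functional improvement. If early groups are prompted only towards harm from poor care, such a result could look more anomalous than open questioning would have made it.

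**Working it through.** No error rate or sample-size formula applies, because Aim 1 is wholly qualitative. The check sets the aim, the draft questions and the analysis plan side by side.

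**1. Each draft question against the five comparators**

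| Appendix E question | Comparators covered | Form |
|---|---|---|
| 1 | 1 (coordination and quality) and 2 (access) | asks how; effect assumed, mildly |
| 2 | 3 (technical skill) and 4 (interpersonal skill) | asks how; effect assumed, mildly |
| 3 | 5 (information) only | effect asserted outright |

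Counts:
- Questions that presuppose an effect: 3 of 3.
- Questions that ask whether a problem has been experienced: 0 of 3.
- Comparators that share a question: 2 + 2 = 4 of 5. Information has its own question, so Question 3 shows the leading wording but not the pairing.
- Questions on PWD versus PWOD: 0 of 3. The draft survey in Appendix B does not ask about this either.

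**2. Reach.** The Second Life groups are the VAI and Clinician groups together, and the Urban group uses their guide. That gives 3 + 2 + 1 = 6 groups, all of the Aim 1 groups. No group is planned with a differently framed guide.

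**3. Whether planned steps would remove the problem**
- The rewrite is aimed at readability and clarity. A leading question can be put into plainer words and still lead.
- The design groups are asked what each question seems to be asking and whether other questions matter. This could bring in extra items, but it is not a check for neutrality.
- Some codes are set in advance by comparator, most emerge from the data, and transcripts are double-coded. This helps to separate comparators within an answer. It works only on what was said, so it cannot restore an experience the prompt did not draw out.

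**4. The Aim 1 paragraph itself.** Its two example questions also ask how rather than whether. Copying the PWD and PWOD question into the guide unchanged would bring in the same presupposition.

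**5. Time.** Groups officially last one hour. Ignoring the closing question, three questions leave 60 / 3 = 20 minutes each. Five comparator questions plus the disability comparison leave 60 / 6 = 10 minutes each, or 10 × 60 / 8 = 75 seconds per person with eight members. Keeping three blocks, with a separate probe for each comparator, and adding the comparison as a fourth leaves 60 / 4 = 15 minutes per block.

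**The case against.** The strongest reply is that these are draft examples and not a fixed script. Where the leader's standardized role is described, the text points to the instructions in Appendix A. Those were not in the text available for this check, so neutral prompts there cannot be ruled out. Clinicians cannot be asked about their own chance of self-care as the questions are worded, so some adaptation is clearly expected. A pilot will test group procedures. Participants may pass on a question, are asked for examples, and can volunteer dissent. The disability comparison is already planned in the Aim 1 paragraph. The existence or non-existence of disparities is left to the quantitative work on Medicare Current Beneficiary Survey data, which a moderator's wording cannot alter.

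Most of this stands, and it limits the point. A reader might infer that the groups cannot report an absence of problems, cannot distinguish the comparators, or will confirm the study hypothesis by construction. The documents do not support that: open discussion, requested examples, comparator-based and emergent codes, double coding and member checking all leave room for contrary and separable answers. The reply does not remove the mismatch between the aim and the only Aim 1 question list in the guide, and none of these steps is directed at neutrality.

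A reader might also count the later Recommendations scenario as part of the same fault: "Our research shows that when people who have disabilities receive high quality healthcare that this may reduce the chance of their disabilities getting worse". That is a secondary matter. It is labelled an example, is hedged, and is to give way to scenarios drawn from the simulations. The opposing improvement result has already been discussed with stakeholders and might still be presented. The point does not rest on it.

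**Conclusion.** The point holds as one of bias and weakened separation. All three draft Aim 1 questions presuppose an effect, one of them outright. Four of five comparators are asked about only in pairs, and the planned disability comparison is missing from the guide. All six Aim 1 groups would be exposed if the draft wording were used as it stands. The size of the resulting bias in the themes cannot be calculated from the documents.

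The conclusion assumes that the Appendix E wording survives the readability rewrite in substance, and that Appendix A does not already supply neutral prompts. If either assumption fails, the point shrinks accordingly. The change is worth making before Aim 1 because the themes feed later hypotheses and the draft is open for revision anyway.

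**What to change.** During the rewrite already planned before Aim 1:

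- Replace the three questions with neutral prompts, for example: *What have your experiences been with [comparator]? Did they make things better, worse or no different for caring for yourself or living independently?*
- Name each of the five comparators separately, as its own question or, if the hour is tight, as a separate probe within a shared block.
- Carry the PWD and PWOD question into the guide, worded as whether care differs and, if so, how.
- Prepare a version for the Clinician groups that refers to their patients and practice.
- Give the design groups and the pilot the added task of checking that a participant can comfortably answer that there was no problem or no difference.

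The cost is editing a draft appendix and somewhat less discussion time per question: about 10 minutes each with six separate questions, or about 15 minutes per block if probes are used, against about 20 now.
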